**The following assessments should be performed at each evaluation i.e (every 8 weeks):**

- Tumor markers CEA (Carcino-Embryogenic Antigen), CA 19.9 (Carbohydrate Antigen 19-9)
- Radiological tumor assessment using the RECIST criteria, version 1.1 (see appendix 4) must be performed. (CT scan of the abdomen, pelvis and chest or hepatic MRI and CT scan of the pelvis and chest without injection)
- Physical examination with weight, BSA

- Three 7-ml EDTA tubes for cfDNA (not supplied). After centrifugation, the plasma will be frozen at -80°C until shipment.

## 5.4 End of treatment Visit

The end of treatment corresponds to the last treatment administered.

When a patient is taken off treatment, the following assessments should be performed within 14 days after study treatment has stopped provided the last clinical and laboratory evaluations > 7 days.

- Physical examination with weight, BSA
- ECOG performance status
- Adverse events documentation (including Start/Stop dates, seriousness, CTC notation and grading, relationship to study drug, outcome and action taken) using CTCAE V5.0
- Concomitant medications
- 12-lead ECG
- A CBC with differential should be performed: RBC, hemoglobin, hematocrit, platelet count and WBC. WBC must include differential neutrophil, lymphocyte, monocyte, basophil and eosinophil counts
- Coagulation panel: Prothrombin time (PT) or the International Ratio of PT (PT-INR) and Partial Thromboplastin Time (PTT)
- Electrolyte panel: sodium, potassium, calcium, magnesium and chloride
- Chemistry panel : albumin, lipase, phosphate, glucose, serum creatinine, clearance calculated according MDRD, uric acid, protein total,

- Liver function test panel: Aspartate Amino-Transferase (AST), Alanine Amino-Transferase (ALT), bilirubin (total and direct), GGT, alkaline phosphatase, Lactic Dehydrogenase (LDH)
- Tumor markers: CEA (Carcino-Embryogenic Antigen), CA 19.9 (Carbohydrate Antigen 19-9)
- Three 7-ml EDTA tubes for cfDNA (not supplied). After centrifugation, the plasma will be frozen at -80°C until shipment.
- Urine analysis: PH, protein, glucose, bilirubin, ketones, blood cells and leukocytes
- A radiological tumor assessment using the RECIST criteria, version 1.1 (see appendix 4) must be performed if the last radiological assessment > 1 months. (CT scan of the abdomen, pelvis and chest or hepatic MRI and CT scan of the pelvis and chest without injection)
- The blood pressure will be recorded by the patient and entered onto his treatment diary. Blood pressure measurements will be performed in patients sitting for 5 minutes prior to the evaluation.
- Drug accountability (pharmacy)
- Patient's diary checking

## 5.5 Follow-up

### Safety Follow-Up Visit

Patients have to be evaluated for symptoms and adverse events in a visit **30 days (+/- 7 days)** after permanently stopping study treatment. This contact may be completed via telephone. The following assessments should be performed:

- Vital status
- Anti-cancer medications
- Physical examination

- A radiological tumor assessment using the RECIST criteria, version 1.1 (see appendix 4) must be performed if only it weren't performed at the end of treatment visit.  
(CT scan of the abdomen, pelvis and chest or hepatic MRI and CT scan of the pelvis and chest without injection).
- Tumor markers : CEA (Carcino-Embryogenic Antigen), CA 19.9 (Carbohydrate Antigen 19-9) if not done at the EOT visit
- Concomitant medications (including anti-cancer medication)
- Adverse events documentation
- The blood pressure must be performed if only it weren't performed at the end of treatment visit.

#### **Follow-up every three months for 3 years**

- Vital status
- Anti-cancer medications
- Physical examination
- Adverse events documentation (only for unstabilized adverse events since the end of treatment)

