**Prophylactic G-CSF will be systematically given after each course from Day-7 to Day 12.**

**REGORAFENIB** will be given orally at a dose of 80 to 160 mg, as per dose-level, once daily on days 4 to 10 of each cycle

Tumor assessments (computed tomography (CT) or magnetic resonance imaging (MRI)) of the chest, abdomen, pelvis (if patient allergic to iodine contrast agents) will be performed at the baseline, every 8 weeks thereafter.

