Including skin assessment for toxicities

Pre-menopausal women of childbearing potential only

12-lead ECG will be performed before and after the administration of Oxaliplatin during the three first cycles (Phase I and II) beyond cycle 3, ECG will be performed before administration of oxaliplatin

Includes: albumin, creatinine, creatinine clearance calculated according MDRD, lipase, glucose, TSH (every 6 weeks of CXD1), , total protein and uric acid

Liver function tests will be performed weekly during the three first cycles of treatment

Not required at day 1 of cycle 1 if those were completed within 7 days

Dipstick assessment with pH, protein, glucose, bilirubin, ketones, blood cells and leucocytes

CT scan of the abdomen, pelvis and chest or if the patient is allergic to iodine contrast agents, hepatic MRI and CT scan of the pelvis and chest without injection; RECIST criteria version 1.1

CT-Scans will be performed every 8 weeks

If the last radiological tumor assessment > 1 month

CT-Scan of safety follow-up will be performed if only it weren't done at the EOT visit

Period for DLT assessment is the three first cycles (only Phase I)

Height only at screening

Blood pressure will be monitored every other week during the first 3 cycles of treatment

Continuously from screening until FU visit, 30 days after last administration of study drug

A treatment diary will be handed over to patient on cycle 1 day 1

Three EDTA tubes will be collected at baseline, every 8 weeks during treatment and at the end of treatment

Paraffin-embedded human solid tissue blocks will be sent off at room temperature at the end of the enrollments

Only for unstabilized adverse events since the end of treatment

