## 9. Subject withdrawal/end of study

### 9.1. DISCONTINUATION OF TREATMENT

Discontinuation of treatment does not represent withdrawal from the trial. As certain data on clinical events beyond treatment discontinuation are important to the study, they must be collected through the subject's last scheduled follow-up, even if the subject has discontinued treatment. Therefore, all subjects who discontinue trial treatment prior to completion of the treatment regimen will still continue to participate in the trial.

Patient may be discontinued from study treatment at any time if the patient, the Investigator, or the Sponsor feels that it is not in the patient's best interest to continue on study. The following is a list of possible reasons for early discontinuation of study treatment:

- Disease progression (unless there is reasonable evidence of clinical benefit to justify continuation on treatment – to be discussed with the Sponsor)
- In the investigator's opinion, continuation in the study treatment would be detrimental to the patient's well-being
- Protocol violation requiring discontinuation of study treatment
- Patient is not compliant with study procedures
- Patients with a β-HCG test consistent with pregnancy. Pregnancy will be notified to the sponsor.
- Any adverse event that cannot be adequately managed with dose modifications, including dose interruption > 28 days (unless there is reasonable evidence of clinical benefit to justify continuation on the protocol – to be discussed with the Sponsor)
- Discontinuation of treatment during more than 4 weeks
- Patient death
- New cancer
- Lost to follow-up

(The Investigators should make every effort to recontact the patient to identify the reason why he/she failed to attend the visit, and to determine the patient health status, including at least the vital status. Attempts to contact such patients must be documented in the patient's records (e.g., times and dates of attempted telephone contact, receipt for sending a registered letter).

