## 9.4. ASSESSMENT CRITERIA

Phase I: Identify the maximum-tolerated dose (MTD) of Folfirinox combination with regorafenib in Patients with metastatic colorectal cancer.

Phase II:

Non-progression rate (OR+SD): The tumor response will be assessed by the investigator using RECIST guidelines v1.1 (2009). The non-progression rate will be presented as a percentage with a 95% confidence interval.

Objective response (OR): The tumor response will be assessed by the investigator using RECIST v1.1 criteria, from the first course of chemotherapy, until disease progression. Patients with suggestive symptoms of disease progression should be evaluated at the time of onset of symptoms. An objective response is defined as a complete (CR) or a partial (PR) response.

The best objective response rate will be reviewed at the end of treatment and presented as a percentage with a confidence interval of 95%.

Survival:

Progression-free survival (PFS): Survival Delays will be calculated in months from the date of inclusion to the date of the considered event: First documented disease progression or death from any cause.

Living patients without disease progression will be censored at the last known date.

Rates and median PFS will be estimated using Kaplan-Meier method and presented with its 95% confidence interval.

Overall survival (OS): The overall survival time will be calculated in months from the date of inclusion to the date of death from any cause. Living patients will be censored at the last known date.

Rates and median overall survival will be estimated using the Kaplan-Meier product limit method and presented with its 95% confidence interval.

The median follow-up will be calculated using the "reverse Kaplan-Meier method".

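### The sections conflict on tumour imaging after treatment stops, so a patient who stops without progression before week 48 may have no week-48 scan for the primary endpoint

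*Combined protocol and SAP*

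**What the plan says.** **Endpoint.** Section 2.2.1 takes the proportion of all treated patients who are non-progressing at week 48 after central review. Progression or death before then is a failure. No sentence deals with a living, non-progressed patient who has no week-48 scan. Section 7 sends the CT scans of patients found progression-free at week 48 for review.

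**Visit schedule.** Section 5.3, on the treatment period, lists radiological assessment among the 8-weekly evaluations, and a footnote to the table in 5.1 says "CT-Scans will be performed every 8 weeks". At the end-of-treatment visit (5.4) a scan "must be performed if the last radiological assessment > 1 months". At the 30-day safety visit (5.5) one "must be performed if only it weren't performed at the end of treatment visit". The later programme, "Follow-up every three months for 3 years", covers vital status, anti-cancer medication, physical examination and unstabilised adverse events, with no imaging. The table has no tumour-assessment mark for it either.

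**Text pointing the other way.** The synopsis, under treatment modalities, says CT or MRI "will be performed at the baseline, every 8 weeks thereafter". Section 9.4 assesses objective response "from the first course of chemotherapy, until disease progression". Section 9.1 says that "all subjects who discontinue trial treatment prior to completion of the treatment regimen will still continue to participate in the trial".

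**Who is off treatment.** Section 6.4 plans 12 cycles. Regorafenib then continues only in patients who have not progressed and remain unresectable. Section 9.1 also foresees stopping for adverse events or for an interruption of more than 4 weeks.

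**Analysis sets.** Section 10.2 treats a patient as evaluable with a week-48 evaluation, or without one if progressed or dead. Section 10.1 requires at least 29 successes among 65 evaluable patients, with 69 included to allow for 5% non-evaluable.

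**The concern.** Section 5 is the part a site works from visit by visit. Followed item by item, it lets imaging end soon after treatment does, while the endpoint needs imaging at a fixed 48 weeks from the start of therapy.

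The patients exposed are not a random sample. One group is patients resected by the end of cycle 12, who get no maintenance and are likely to include good responders. The other is patients who stop all treatment for toxicity. The second group is limited, because several dose rules in section 6.6 stop one drug and continue the others.

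Missing status could therefore be related to outcome. In the all-treated analysis such a patient sits in the denominator and cannot be a reviewed success. The per-protocol set drops this patient but keeps progressors and deaths. Section 10.3 promises a later analysis plan, which can settle the counting but cannot recover scans that were not taken.

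**Working it through.** **1. Plan's own figure.** Inputs from section 10.1: p0 = 0.35, p1 = 0.50, α = 5% (taken as one-sided, which reproduces N), β = 20%.

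n = [(1.645·√(0.35·0.65) + 0.842·√(0.50·0.50)) / 0.15]² = 64.57, rounded up to 65. Then 65/0.95 = 68.4, rounded up to 69. Both stated figures reproduce.

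Exact binomial for the rule of at least 29 of 65: P(X ≥ 29 | 0.50) = 83.9% and P(X ≥ 29 | 0.35) = 6.9%. That the second figure exceeds 5% is a property of the cut-off and a separate matter. It serves here only as a baseline.

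**2. Latest scheduled scan** (sections 5.4, 5.5, 6.1 and 6.4; 14-day cycles, regorafenib on days 4 to 10):

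- Twelve uninterrupted cycles, no maintenance: last dose on day 11·14 + 10 = 164 (week 23.4). Latest safety-visit scan on day 164 + 37 = 201 (week 28.7). Gap to week 48: 19.3 weeks. The scans at weeks 32, 40 and 48 are not scheduled.
- One surgical break, then completion of 12 cycles: 4 weeks before the procedure plus 4 to 8 weeks after it, replacing one 2-week interval, adds 6 to 10 weeks. Latest scan at 28.7 + 6 = 34.7 to 28.7 + 10 = 38.7 weeks. Gap: 13.3 to 9.3 weeks. The scans at weeks 40 and 48 are not scheduled.
- Early stop for toxicity: earlier than week 28.7, with more scans unscheduled.
- Regorafenib maintenance through week 48: no gap.

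**3. Possible effect.** The documents give no resection or toxicity-stop rate, so the shares below are assumptions. The rule stays at 29 of 65.

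*Share f of true successes without status, true rate 50%.* Counted as failures, the observed rate is 0.50(1−f). Excluded, with 65 evaluable still reached, it is 0.50(1−f)/(1−0.50f).

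| f | Counted as failures: rate, power | Excluded: rate, power |
|---|---|---|
| 0% | 0.500, 83.9% | 0.500, 83.9% |
| 5% | 0.475, 72.2% | 0.487, 78.4% |
| 10% | 0.450, 57.2% | 0.474, 71.5% |

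*Share m of all patients excluded, of whom a share s are true successes, true rate 35%.* The rate among those kept is (0.35 − m·s)/(1 − m). The table gives the chance of declaring success (baseline 6.9%).

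| m | s = 20% | s = 35% | s = 50% |
|---|---|---|---|
| 5% | 8.9% | 6.9% | 5.3% |
| 10% | 11.6% | 6.9% | 3.8% |

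Exclusion does no harm to the error rate when the missing patients resemble the rest. Otherwise it moves the rate in either direction.

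**The case against.** The strongest reply is that the protocol does intend week-48 imaging. The synopsis sets 8-weekly scans with no stop at end of treatment, and week 48 is the sixth of them. Sections 2.2.1, 7 and 10.2 all presuppose a week-48 evaluation, and 9.1 keeps patients off treatment in the trial. This stands as far as it goes. A reader might infer from section 5 that the protocol plans no imaging after treatment for anyone, and the documents do not support that. What they show is a conflict: none of the broader statements gives off-treatment scan dates, and the itemised follow-up list omits imaging.

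Three other strong readings also fail:

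- *Unscanned patients could pass as non-progressing and inflate the success rate.* Section 2.2.1 requires central review, and there would be no week-48 scan to review. Upward bias needs exclusion under section 10.2 and missing patients who succeed less often than average.
- *Every resected patient has a 19-week gap.* That figure belongs to 12 uninterrupted cycles without maintenance. Section 6.4 has a patient resected mid-treatment pause and resume, which gives roughly 9 to 13 weeks.
- *The loss of power is established.* It rests on assumed shares, and in the power table every missing patient is a true success.

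The plan does allow for 5% non-evaluable patients. That protects the number evaluable, but not against selective missingness. Sites may also scan these patients as routine care, but section 5 does not require it.

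**Conclusion.** The point holds as a conflict between sections that bears on the primary endpoint. A site complying with the visit schedule could leave a patient who stops without progression before week 48 with no week-48 scan. The timing follows from the protocol's own intervals, given the assumed surgical break of 4 weeks before and 4 to 8 weeks after the procedure.

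The likely effect in the all-treated analysis is a success rate biased downward. In the per-protocol set the direction is open. The size is unknown: the power figures show sensitivity to assumed missingness and are not a forecast. Exposure is narrow, since maintenance patients keep their scans and many toxicity rules drop only one drug. It should still be corrected, because the loss cannot be repaired at analysis.

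**What to change.** 1. In sections 5.3 to 5.5 and the table in 5.1, state that 8-weekly tumour assessment continues until progression or week 48 for every treated patient, on or off treatment. This brings the schedule into line with the synopsis and section 9.4.
2. In section 2.2.1, state that a treated patient with no week-48 scan and no documented progression counts as a failure in the primary analysis, and add a sensitivity analysis with another handling of these patients.

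The cost is protocol wording plus a few standard CT scans on the existing calendar, only in patients who stop without progression before week 48. Most would need two (weeks 40 and 48) or three (weeks 32, 40 and 48), and more after an early stop. No new procedure is needed, and the planned 65 evaluable and 69 included are unchanged.

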#### **5.6 End of study**

- Paraffin-embedded human solid tissue blocks will be sent off at room temperature at the end of the enrollments.

### **6. Treatments**

#### **6.1 Experimental treatment or procedures**

Patients having signed informed consent form will receive after registration the treatment.

Patients are eligible for repeated treatment cycles in the absence of disease progression and non-manageable adverse events.

The IV investigational products (IP) will be prepared according to the chemotherapy safety standards (appendix 6).

### **FOLFIRINOX administration (Phase I and II):**

**FOLFIRINOX** will be administered as per standard procedures: every 14 days (**1 cycle = 14 days**):

- Oxaliplatin (Eloxatin® or generic drug): 85mg/m^2 on day 1, IV infusion over 2 hours, immediately followed by
- Folinic acid 400 mg/m^2 or Calcium Levofolinate 200mg/m^2 given as a 2-hour IV infusion, with the addition, after 30 minutes of
- Irinotecan (Campto® or generic drug): 150-180 mg/m^2 as per dose-level, given as a 90-minute intravenous infusion through a Y-connector immediately followed by
- 5-Fluorouracil: 400mg/m^2 IV bolus then 2400mg/m^2 over 46 hours continuous infusion.

Irinotecan infusion has to be preceded by a subcutaneous injection of atropine: 0.25mg to prevent cholinergic syndrome (in absence of contraindication).

[figure not shown]
The next cycle starts on day 15. Each cycle will be delivered every 2 weeks.

**With this treatment, prophylactic G-CSF will be systematically given after each course from Day 7 to Day 12.**

### **REGORAFENIB administration (Phase I and II):**

-On days 4–10 of each cycle, all patients will receive Regorafenib orally once daily depending on dose levels for phase I and RPD2 for phase 2.

- 1 cycle = 15 days

## **6.2 Drug packaging and labelling**

### **5-FU, Oxaliplatin, Irinotecan**

Oxaliplatin, irinotecan, 5-Fluorouacil and calcium levofolinate will be taken in the usual stock.

## **Regorafenib**

For List of excipients and Storage: See Investigator's brochure (appendix 7).

The investigational drug regorafenib must be exclusively used for the investigation specified in this protocol, and it will only be accessible to authorized staff. The sponsor delegate labelling, packaging and shipping of product during the study to Sodia. Sodia will perform this prestation in accordance with applicable Good Manufacturing Practices.

Regorafenib will be provided by Sponsor as film-coated tablets of 40 mg in 30-tablet bottles.

The investigational product(s) label will bear sponsor's name, address and telephone number, the EudraCT number, product name, dosage form and strength, batch number, expiration date, required storage conditions and required caution statements as applicable.

### **6.3 Shipment, storage conditions and accountability and destruction**

The experimental drug regorafenib, provided by the sponsor, will be distributed to the pharmacy at the investigational center by Sodia in accordance with the current Good Distribution Practices guidelines.

The pharmacist of the trial site will receive numbered treatment and will acknowledge receipt of all the shipments by sending to the distributor a form duly completed.

Investigational medicinal products will have to be stored in locked room with limited access and in accordance with the recommendations of the manufacturer.

The pharmacist of the health care site will keep accurate records of the drugs delivered, used, unused or destroyed.

The clinical research assistant mandated by the sponsor will be in charge of verifying the accounting records for the supplied medicinal products and ensure that an accounting form is validated and signed by the pharmacist of the health care center prior to any demand for destruction.

Sites will be provided with an initial supply when activated, and after sites can order supplies as and when they need them. A form will be provided to the site when they are activated.

The pharmacist is responsible for a safe and proper handling and storage of the investigational medicinal products at the investigational center. The investigational products must be stored in a locked facility with restricted access to the pharmacist and authorized personnel, and under environmental conditions consistent with the drug manufacturer recommendations (SmPC for FOLFIRINOX or IB for Regorafenib).

**Storage requirements of regorafenib:** Regorafenib bottles must be stored in the original carton under refrigeration at a temperature between 2°C and 25° C until the time of use. Bottles will be kept tightly closed.

**Storage requirements of irinotecan:** Irinotecan must be kept in the outer carton in order to protect from light.

The Irinotecan concentrate for solution for infusion should be diluted and used immediately after opening. However, if dilution takes place in controlled and validated aseptic conditions, the Campto® solution for infusion can be used (infusion time included) within 12 hours when stored at room temperature, or within 24 hours when stored in a refrigerator at 2°C to 8°C after dilution/reconstitution.

**Storage requirements of oxaliplatin:** after dilution in 5% glucose, chemical and physical in-use stability has been demonstrated for 48 hours at +2°C to +8°C and for 24 hours at +25°C. From a microbiological point of view, this infusion preparation should be used immediately. If not used immediately, in-use storage times and conditions prior to use are the responsibility of the user and would normally not be longer than 24 hours at 2°C to 8°C unless dilution has taken place in controlled and validated aseptic conditions.

**Storage requirements of 5-Fluorouracil:** do not store above 25°C. Keep container in the outer carton to protect from light. Do not refrigerate.

Store the preparation at a temperature between + 15°C and +25°C. After dilution, immediate use is recommended. However, chemical and physical in-use stability has been demonstrated for 8 hours at a temperature between + 15°C and +25°C.

**Storage requirements of calcium levofolinate:** The lyophilisat must be kept at a temperature <30°C, protected from light and humidity. After preparation, the solution may be kept for 24 hours below 30°C. It may be conserved longer in a refrigerator at a temperature between 2°C and 8°C and in the dark.

All Temperature excursions relating to the shipping or storage of regorafenib (in line with the below table 3) will be reported to ICM as soon as the site becomes aware. In terms of what constitutes a temp excursion for regorafenib, this is summarized below:

